10. Creatine Kinase: Scheduled CK tests are only drawn at screening, baseline, and, annually thereafter. If a subject complains of muscle discomfort at a visit, a CK level should be drawn. If at any time a CK level is > 5X the upper limit of normal (ULN), an unscheduled visit should be scheduled for a repeat CK, within 48 hours if possible, with CK fractionation for isozymes (to assess CK-MM and CK-MB) and urine dipstick. Unscheduled measurements of CK do not require fasting. See [Section 7.2.5](#), [Section 7.6](#) and [Appendix 7](#).  
Prior to obtaining blood for a CK assessment, investigators should enquire about recent intramuscular injections, heavy exercise, or recent musculoskeletal trauma, and defer CK testing until the next visit or repeat testing at an unscheduled visit, no less than 7 days after the IM injection or musculoskeletal trauma, so as to avoid spuriously elevated values.
11. ADA/PK/PCSK9 sampling: Anti-drug antibody (ADA), bococizumab drug, and PCSK9 blood samples should be collected in all subjects, at the baseline and designated visits as described in [Section 6](#). For Visit 3, only a PCSK9 sample is needed. No PK or ADA sample is needed at Visit 3. After randomization, if lipid sampling has been postponed to an unscheduled visit, the corresponding ADA/PK/PCSK9 samples should be postponed as well, and collected at the same time as the rescheduled lipid sample collection. ADA, PK, and PCSK9 samples will be collected at EDC/EOS visits.
12. Hematology: Complete blood count (CBC) with white blood cell (WBC) and red blood cell (RBC) counts, hemoglobin, hematocrit, WBC differential and platelet count. All hematology studies are to be performed by central laboratory.
13. Urinalysis: Dipstick urinalysis will be performed by study site, locally. Details describing what is evaluated in the urinalysis are described in [Section 7.2.1.2](#), [Table 2](#). At the screening visit a central lab urine albumin/creatinine ratio assessment may be evaluated, in subjects who have had a cardiovascular event more than 5 years prior to screening and in subjects without a prior qualifying cardiovascular event.

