5.4.2.4. Subgroups for Pharmacokinetics/Pharmacodynamics

Summaries and plots of LDL-C response will be done in subgroups defined by the following variables, except as noted below. The definitions of anti-drug antibody (ADA) and neutralizing antibody (nAb) status, ADA and nAb duration response type and ADA and nAb titer response type are provided in [Section 6.2](#).

- Treatment with bococizumab and ADA status;
 - Treated Bococizumab Subjects With Positive ADA Status; Treated Bococizumab Subjects With Negative ADA Status.

- Treatment with bococizumab and pre-treatment ADA result;
 - Treated Bococizumab Subjects With Pre-Existing Antibodies; Treated Bococizumab Subjects Without Pre-Existing Antibodies.
- Treatment with bococizumab and nAb status;
 - Treated Bococizumab Subjects With Positive nAb Status; Treated Bococizumab Subjects With Negative nAb status.
- Treatment with bococizumab and duration of ADA response type;
 - Treated Bococizumab Subjects with Indeterminate Duration of ADA Response; Treated Bococizumab Subjects with Persistent Duration of ADA Response; Treated Bococizumab Subjects with Transient Duration of ADA Response.
- Treatment with bococizumab and duration of nAb response type;
 - Treated Bococizumab Subjects with Indeterminate Duration of nAb Response; Treated Bococizumab Subjects with Persistent Duration of nAb Response; Treated Bococizumab Subjects with Transient Duration of nAb Response.
- Treatment with bococizumab and ADA titer response type;
 - Treated Bococizumab Subjects with Negative ADA status; Treated Bococizumab Subjects with Positive ADA Status and Maximum ADA Titer in the 1st Tertile; Treated Bococizumab Subjects with Positive ADA Status and Maximum ADA Titer in the 2nd Tertile; Treated Bococizumab Subjects with Positive ADA Status and Maximum ADA Titer in the 3rd Tertile.
- Treatment with bococizumab and nAb titer response type;
 - Treated Bococizumab Subjects with Negative nAb status; Treated Bococizumab Subjects with Maximum nAb Titer in the 1st Tertile; Treated Bococizumab Subjects with Maximum nAb Titer in the 2nd Tertile; Treated Bococizumab Subjects with Maximum nAb Titer in the 3rd Tertile.

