8.2.4.1.1. Definitions

ADA and nAb titers are provided to Pfizer in log₂ format and will be reported in the same manner. All titles and labels used in tables and figures should clearly indicate titer (log₂).

ADA Measurement Level Status:

An ADA measurement is considered as ADA positive if the ADA titer ≥ 6.23 ; otherwise if non-missing, the measurement is considered as ADA negative.

nAb Measurement Level Status:

An nAb measurement is considered as nAb positive if the nAb titer ≥ 1.58 (Assay #2). An nAb measurement is considered as nAb negative if the ADA measurement from that sample is negative or if the nAb titer < 1.58 .

ADA Subject Level Status – For subject level classification of ADA (positive, negative):

A subject will be considered ADA positive if:

- The subject is ADA negative at baseline and has at least 1 ADA positive post-dose measurement, or
- The subject is missing the baseline ADA measurement and has at least 1 ADA positive post-dose measurement, or
- The subject is ADA positive at baseline and has a >1.58 unit increase in ADA titer from a positive baseline titer in at least 1 post-dose measurement.

A subject will be considered ADA negative if:

- The subject is ADA negative at baseline and all post-dose measurements are negative, or
- The subject is missing the baseline ADA measurement and all post-dose measurements are negative, or
- The subject is ADA positive at baseline but does not experience >1.58 unit increase in titer from a positive baseline titer in any post-dose measurement.

nAb Subject Level Status – For subject level classification for nAb (positive or negative):

A subject will be considered nAb positive if:

- The subject is nAb negative at baseline and has at least 1 nAb positive post-dose measurement, or
- The subject is missing the baseline nAb measurement and has at least 1 nAb positive post-dose measurement, or

- The subject is nAb positive at baseline and has a >1.58 unit increase in nAb titer from a positive baseline titer in at least 1 post-dose measurement.

A subject will be considered nAb negative if:

- The subject is ADA negative, or
- The subject is nAb negative at baseline and all post-dose measurements are nAb negative, or
- The subject is nAb positive at baseline but does not experience a >1.58 unit increase in titer from a positive baseline titer in any post-dose measurement.

ADA (nAb) Response Type:

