8.2.4.3. Summarization of Pharmacokinetics/Pharmacodynamics Results

The following analyses will be performed for LDL-C response. The windows from [Table 3](#) in [Appendix 1.1](#) will be used.

The following summaries will be provided using only observations meeting the following conditions (without missed doses and prior to dose adjustment):

- Sample collection date minus the previous injection date is between 1 and 21 days.
 - No dose adjustments have occurred prior to sample collection.
1. For LDL-C, the descriptive summaries will be repeated by ADA status and by nAb status. Box plots of percent change from baseline will be repeated by ADA status and by nAb status.
 2. For LDL-C, the descriptive summaries will be repeated by duration of ADA response (indeterminate/persistent/transient) and by duration of nAb response (indeterminate/persistent/transient). Box plots of percent change from baseline will be repeated by duration of ADA response (indeterminate/persistent/transient) and by duration of nAb response (indeterminate/persistent/transient).
 3. For LDL-C, the descriptive summaries will be repeated by pre-existing ADA status (with pre-existing ADAs, without pre-existing ADAs).
 4. For LDL-C, the descriptive summaries will be repeated by ADA (nAb) titer response (ADA (nAb) negative, ADA (nAb) 1st tertile, ADA (nAb) 2nd tertile, ADA (nAb) 3rd tertile).

A comprehensive listing of LDL-C, ADA status, ADA titer, nAb status, and nAb titer will be provided by subject and visit for ADA positive subjects.

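### LDL-C by visit is summarised only by subject-level antibody labels, so values from before seroconversion count as antibody-positive; add a summary by status at the time of the sample

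*SAP*

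**What the plan says.** SAP 5.4.2.4 sets the grouping: "Summaries and plots of LDL-C response will be done in subgroups defined by the following variables". The first pair is "Treated Bococizumab Subjects With Positive ADA Status; Treated Bococizumab Subjects With Negative ADA Status". The others are nAb status, pre-existing antibodies, duration of response, and maximum titer, for example "Treated Bococizumab Subjects with Positive ADA Status and Maximum ADA Titer in the 1st Tertile". All are groups of subjects, not of samples.

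SAP 8.2.4.1.1 defines the labels. For a subject negative at baseline, the criterion for being ADA positive is: "The subject is ADA negative at baseline and has at least 1 ADA positive post-dose measurement". A missing baseline is treated the same way, and nAb follows the same pattern. Subjects already positive at baseline have a different criterion: "The subject is ADA positive at baseline and has a >1.58 unit increase in ADA titer from a positive baseline titer". Without that rise they count as negative. A subject whose first positive is more than 14 days after the last dose is still a positive subject, classed as off-treatment.

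SAP 8.2.4.3 applies these labels to LDL-C in the Table 3 visit windows: "For LDL-C, the descriptive summaries will be repeated by ADA status and by nAb status". It keeps only LDL-C values taken 1 to 21 days after the previous injection and before any dose adjustment.

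On sampling, Protocol Schedule of Activities footnote 11 says that if a lipid sample is postponed, "the corresponding ADA/PK/PCSK9 samples should be postponed as well, and collected at the same time as the rescheduled lipid sample collection".

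**The concern.** The label is fixed using the whole follow-up and then applied backwards. A subject first positive at Week 40 is in the positive column, possibly the top titer tertile, at Weeks 4 and 14, when the samples were negative. A subject first positive only after treatment ended carries the positive label on every on-treatment LDL-C value.

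These are the SAP's only planned summaries of LDL-C response by antibody status. If antibodies blunt LDL-C lowering, a table that mixes pre- and post-seroconversion values in one column understates the loss at visits where many eventual positives have not yet converted, and blurs when it begins. The Protocol (1.2.3) reports ADAs in 42.5% (201/473) of exposed subjects in three earlier studies, so the group concerned could be large.

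**Working it through.** The plan states no figure for this comparison, so there is none to reproduce. The check has two parts: whether the rule works as described, and how much it could matter.

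**1. Tracing the rule.** SAP 5.4.2.4 groups LDL-C by subject status. It points to Section 6.2 for the definitions, but they are in 8.2.4.1.1. There, one positive post-dose sample at any time suffices for baseline-negative or baseline-missing subjects. Neither filter in 8.2.4.3 refers to the date of the first positive sample, so pre-seroconversion LDL-C stays in. Section 8.2.4.1.1 also defines ADA and nAb status for each measurement, but no LDL-C summary uses it.

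**2. The mixture.** At a given visit let
- f = share of eventual positives already positive;
- D = gap in LDL-C percent change between those already positive and the negatives;
- d0 = gap between eventual positives not yet positive and the negatives.

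Gap shown = f × D + (1 − f) × d0.

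If eventual positives resemble negatives before seroconversion, d0 = 0 and the gap shown is f × D. D is assumed to persist after seroconversion.

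| f | D = 10 | D = 20 | D = 30 |
|---|---|---|---|
| 10% | 1.0 | 2.0 | 3.0 |
| 25% | 2.5 | 5.0 | 7.5 |
| 50% | 5.0 | 10.0 | 15.0 |
| 75% | 7.5 | 15.0 | 22.5 |

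The values of D (percentage points) and f are assumptions.

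**3. A range for f at Week 14.** Assume Weibull onset with shape 1.3 and median m, F(t) = 1 − exp(−ln 2 × (t/m)^1.3). Among subjects positive by horizon H, f = F(14)/F(H).

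| Median m (weeks) | F(14) | H = 104 | H = 52 | H = 40 |
|---|---|---|---|---|
| 12 | 0.571 | 57% | 58% | 59% |
| 26 | 0.267 | 27% | 33% | 38% |
| 40 | 0.162 | 18% | 26% | 32% |

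The shorter horizons are relevant. Protocol 9.1 planned about half of enrolment in the last ten months, the SAP records the program's discontinuation on 01 November 2016, and SAP 8.1.1.2 expects few observations at the last several time points. Subjects with short follow-up can only be labelled from early samples.

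**4. How many subjects.** If 42.5% become positive, those labelled positive but not yet positive at a visit are 0.425 × (1 − f) of bococizumab subjects: 38% at f = 10%, 32% at f = 25%, 21% at f = 50%.

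**5. Simulated check.** Take 8,500 subjects, 42.5% ever positive, D = 20 and exponential onset with mean 20 weeks (all but the 42.5% and the arm size assumed). The subject-level rule gives gaps of 3.6 points at Week 4, 9.5 at Week 14, 14.4 at Week 26 and 19.1 at Week 70. Grouping by status at the visit gives 19.3 to 19.9 throughout.

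**The case against.** **The tables are descriptive.** This stands. Section 8.2.4.3 holds summaries, box plots and a listing, and no test, alpha or decision rule uses them.

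**A reader might infer that the Week 14 LDL-C endpoint is understated.** It is not. SAP 8.2.2 analyses it by MMRM on randomised treatment in the Full Analysis Set, with no antibody grouping.

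**Timing information is already planned.** Largely true. Section 8.2.4.2 gives ADA and nAb results and titers by visit and time to first positive, and 8.2.4.3 ends with a listing of LDL-C, status and titer by subject and visit. But the listing covers only ADA-positive subjects, and none of these summarises LDL-C by status at sampling.

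**Fixed groups are a legitimate display.** They follow the same people over time, so a gap that widens from Week 4 is itself informative about onset. This stands, and is why the subject-level tables should be kept. It would go too far to read the point as calling for their replacement.

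**Time-updated status has its own misclassification.** It does where no ADA sample is scheduled. At Week 26 the latest scheduled result is from Week 14. Under the Weibull assumptions above, 1 − F(14)/F(26) = 33%, 47% or 50% of subjects truly positive at Week 26 would be shown as negative (median 12, 26 or 40 weeks). The added display should therefore rest on visits with scheduled sampling.

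**The SAP already urges caution.** It does so for the adverse event and laboratory subgroups (5.4.2.2 and 5.4.2.3). The note is not in 5.4.2.4 or 8.2.4.3, so it does not cover these tables.

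**Conclusion.** The point holds as a limitation of a descriptive summary. For subjects negative or missing at baseline, LDL-C from before seroconversion is counted as antibody-positive, and the titer tables carry the same problem through the maximum titer. Calling the label ever-positive would be inexact for baseline-positive subjects, who need a rise above 1.58 log2 units.

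Dilution to f × D requires that eventual positives resemble negatives before seroconversion and that the effect persists. Transient positives could dilute later visits too. The figure of roughly 18% to 59% for f at Week 14 is an illustration from an assumed onset curve; a reader might take it as an estimate for this trial, but the documents give neither the timing of seroconversion nor the size of D. The primary, key secondary and Week 14 MMRM analyses are unaffected. The addition is worthwhile because it is cheap and the section's main question is otherwise answered only with fixed labels.

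**What to change.** - Keep the subject-level tables in SAP 8.2.4.3.
- Add LDL-C summaries and box plots of percent change by time-updated status: the ADA and nAb result from the sample drawn with that LDL-C, at visits with scheduled ADA sampling (Weeks 4, 14, 40, 70, 104, 156 and 208).
- For titer, use the titer of that sample, with fixed cut-points pooled across visits so that groups mean the same at every visit.
- At visits without ADA sampling (for example Weeks 8, 26, 52 and 86), either omit this display or show the last earlier result, labelled as carried forward.
- Repeat the post-randomization caution in 5.4.2.4, and correct its cross-reference from Section 6.2 to 8.2.4.1.1.

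No new data are needed: measurement-level status is already defined and ADA is scheduled with lipids at those visits. The cost is SAP wording, a merge of LDL-C with ADA/nAb results by sample date, and a few extra tables and plots. The downside is that column membership changes between visits, so the new display does not follow the same subjects over time.

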8.2.4.4. Adverse Events, Serious Adverse Events, and Deaths

Adverse events and serious adverse events will be summarized by ADA status (positive, negative) and by nAb status (positive, negative).

8.2.4.5. Injection Site Adverse Events

Injection site adverse events will be summarized by ADA status (positive, negative) and by nAb status (positive, negative). The higher level term of “injection site reactions” will be used to identify the adverse events.

8.2.4.6. Clinical Laboratory Measurements

Liver function test elevations will be summarized by ADA status and by nAb status. Additionally, the maximum post-randomization total bilirubin value will be plotted against the maximum post-randomization alanine transaminase (ALT) value by ADA status (positive, negative) and by nAb status (positive, negative).

Incidence of creatinine elevations will be summarized by ADA status (positive, negative) without regard to baseline abnormality, with normal baseline, and with abnormal baseline.

8.2.4.7. Outcomes Research Endpoints

EQ-5D

As a result of the discontinuation of the bococizumab clinical development program, EQ-5D will not be summarized as described in the protocol or listed.

Health Care Resource Utilization

As a result of the discontinuation of the bococizumab clinical development program, health care resource utilization (HCRU) endpoints will not be summarized or analyzed as described in the protocol or listed.

8.2.5. Summary of Efficacy Analyses

Table 2. Tabular Summary of Efficacy Analyses

Endpoint	Analysis Set	Statistical Method	Covariates/ Strata	Objective
Time to major cardiovascular event	FAS	Log rank test	Geographic region, LDL-C at the pre-screening visit (<100 mg/dL, ≥100 mg/dL)	Primary analysis
		Cox proportional hazards regression	Treatment group/ geographic region, LDL-C at the pre-screening visit (<100 mg/dL, ≥100 mg/dL)*	Decision on primary objective
		Plot of Kaplan-Meier Estimates		Support of primary objective
		Arjas plot	Geographic region × complete statin intolerance	
Time to premature discontinuation from the study	FAS	Log rank test	Geographic region, LDL-C at the pre-screening visit (<100 mg/dL, ≥100 mg/dL)	Impact of premature discontinuation from the study
		Cox proportional hazards regression	Treatment group/ geographic region, LDL-C at the pre-screening visit (<100 mg/dL, ≥100 mg/dL)*	
Time to major cardiovascular event	FAS	Multiple imputations for Cox proportional hazards model	Cox model: Treatment group/geographic region Imputation model: Treatment group, age, gender, BMI, geographic region, LDL-C at the pre-screening visit (<100 mg/dL, ≥100 mg/dL), baseline smoking status, baseline history of MI, baseline history of coronary revascularization, baseline history of coronary heart disease, baseline history of diabetes, baseline history of HeFH/LDL-C≥190 mg/dL, baseline history of stroke, baseline history of congestive heart failure baseline history of chronic kidney disease.	Impact of informative censoring under the switch-to-control assumption

Endpoint	Analysis Set	Statistical Method	Covariates/ Strata	Objective
Time to CV death, non-fatal MI or non-fatal stroke	FAS	Log rank test	Geographic region, LDL-C at the pre-screening visit (<100 mg/dL, ≥100 mg/dL)	First key secondary endpoint; tested only if primary objective met
		Cox proportional hazards regression	Treatment group/ geographic region, LDL-C at the pre-screening visit (<100 mg/dL, ≥100 mg/dL)*	Decision on secondary objective
		Plot of Kaplan-Meier Estimates		Support of secondary objective
		Arjas plot	Geographic region × complete statin intolerance	
Time to all-cause death, non-fatal MI, non-fatal stroke, or hospitalization for unstable angina needing urgent revascularization	FAS	Log rank test	Geographic region, LDL-C at the pre-screening visit (<100 mg/dL, ≥100 mg/dL)	Second key secondary endpoint; tested only if primary objective met
		Cox proportional hazards regression	Treatment group/ geographic region, LDL-C at the pre-screening visit (<100 mg/dL, ≥100 mg/dL)*	Decision on secondary objective
Time to all-cause death, non-fatal MI, or non-fatal stroke	FAS	Log rank test	Geographic region, LDL-C at the pre-screening visit (<100 mg/dL, ≥100 mg/dL)	Third key secondary endpoint; tested only if the primary objective is met
		Cox proportional hazards regression	Treatment group/ geographic region, LDL-C at the pre-screening visit (<100 mg/dL, ≥100 mg/dL)*	Decision on secondary objective
Time to hospitalization for unstable angina needing urgent revascularization	FAS	Log rank test	Geographic region, LDL-C at the pre-screening visit (<100 mg/dL, ≥100 mg/dL)	Fourth key secondary endpoint; tested only if primary objective met
		Cox proportional hazards regression	Treatment group/ geographic region, , LDL-C at the pre-screening visit (<100 mg/dL, ≥100 mg/dL)*	Decision on secondary objective
Time to CV death, non-fatal MI, non-fatal stroke, or hospitalization for unstable angina	FAS	Log rank test	Geographic region, LDL-C at the pre-screening visit (<100 mg/dL, ≥100 mg/dL)	Other secondary endpoint

Endpoint	Analysis Set	Statistical Method	Covariates/ Strata	Objective
		Cox proportional hazards regression	Treatment group/ geographic region, LDL-C at the pre-screening visit (<100 mg/dL, ≥100 mg/dL)*	Other secondary objective
Time to CV death	FAS	Log rank test	Geographic region, LDL-C at the pre-screening visit (<100 mg/dL, ≥100 mg/dL)	Other secondary endpoint
		Cox proportional hazards regression	Treatment group/ geographic region, LDL-C at the pre-screening visit (<100 mg/dL, ≥100 mg/dL)*	Other secondary objective
Time to any MI (fatal and non-fatal)	FAS	Log rank test	Geographic region, LDL-C at the pre-screening visit (<100 mg/dL, ≥100 mg/dL)	Other secondary endpoint
		Cox proportional hazards regression	Treatment group/ geographic region, LDL-C at the pre-screening visit (<100 mg/dL, ≥100 mg/dL)*	Other secondary objective
Time to fatal MI	FAS	Log rank test	Geographic region, LDL-C at the pre-screening visit (<100 mg/dL, ≥100 mg/dL)	Other secondary endpoint
		Cox proportional hazards regression	Treatment group/ geographic region, LDL-C at the pre-screening visit (<100 mg/dL, ≥100 mg/dL)*	Other secondary objective
Time to non-fatal MI	FAS	Log rank test	Geographic region, LDL-C at the pre-screening visit (<100 mg/dL, ≥100 mg/dL)	Other secondary endpoint
		Cox proportional hazards regression	Treatment group/ geographic region, LDL-C at the pre-screening visit (<100 mg/dL, ≥100 mg/dL)*	Other secondary objective
Time to any stroke (fatal and non-fatal)	FAS	Log rank test	Geographic region, LDL-C at the pre-screening visit (<100 mg/dL, ≥100 mg/dL)	Other secondary endpoint
		Cox proportional hazards regression	Treatment group/ geographic region, LDL-C at the pre-screening visit (<100 mg/dL, ≥100 mg/dL)*	Other secondary objective

Endpoint	Analysis Set	Statistical Method	Covariates/ Strata	Objective
Time to any stroke (fatal and non-fatal) of any etiology	FAS	Log rank test	Geographic region, LDL-C at the pre-screening visit (<100 mg/dL, ≥100 mg/dL)	Other secondary endpoint
		Cox proportional hazards regression	Treatment group/ geographic region, LDL-C at the pre-screening visit (<100 mg/dL, ≥100 mg/dL)*	Other secondary objective
Time to fatal stroke	FAS	Log rank test	Geographic region, LDL-C at the pre-screening visit (<100 mg/dL, ≥100 mg/dL)	Other secondary endpoint
		Cox proportional hazards regression	Treatment group/ geographic region, LDL-C at the pre-screening visit (<100 mg/dL, ≥100 mg/dL)*	Other secondary objective
Time to non-fatal stroke	FAS	Log rank test	Geographic region, LDL-C at the pre-screening visit (<100 mg/dL, ≥100 mg/dL)	Other secondary endpoint
		Cox proportional hazards regression	Treatment group/ geographic region, LDL-C at the pre-screening visit (<100 mg/dL, ≥100 mg/dL)*	Other secondary objective
Time to hospitalization for unstable angina	FAS	Log rank test	Geographic region, LDL-C at the pre-screening visit (<100 mg/dL, ≥100 mg/dL)	Other secondary endpoint
		Cox proportional hazards regression	Treatment group/ geographic region, LDL-C at the pre-screening visit (<100 mg/dL, ≥100 mg/dL)*	Other secondary objective
Time to hospitalization for congestive heart failure	FAS	Log rank test	Geographic region, LDL-C at the pre-screening visit (<100 mg/dL, ≥100 mg/dL)	Other secondary endpoint
		Cox proportional hazards regression	Treatment group/ geographic region, LDL-C at the pre-screening visit (<100 mg/dL, ≥100 mg/dL)*	Other secondary objective
Time to any coronary revascularization procedure	FAS	Log rank test	Geographic region, LDL-C at the pre-screening visit (<100 mg/dL, ≥100 mg/dL)	Other secondary endpoint
		Cox proportional hazards regression	Treatment group/ geographic region, LDL-C at the pre-screening visit (<100 mg/dL, ≥100 mg/dL)*	Other secondary objective

Endpoint	Analysis Set	Statistical Method	Covariates/ Strata	Objective
Time to CABG	FAS	Log rank test	Geographic region, LDL-C at the pre-screening visit (<100 mg/dL, ≥100 mg/dL)	Other secondary endpoint
		Cox proportional hazards regression	Treatment group/ geographic region, LDL-C at the pre-screening visit (<100 mg/dL, ≥100 mg/dL)*	Other secondary objective
Time to PCI	FAS	Log rank test	Geographic region, LDL-C at the pre-screening visit (<100 mg/dL, ≥100 mg/dL)	Other secondary endpoint
		Cox proportional hazards regression	Treatment group/ geographic region, LDL-C at the pre-screening visit (<100 mg/dL, ≥100 mg/dL)*	Other secondary objective
Time to any arterial revascularization	FAS	Log rank test	Geographic region, LDL-C at the pre-screening visit (<100 mg/dL, ≥100 mg/dL)	Other secondary endpoint
		Cox proportional hazards regression	Treatment group/ geographic region, LDL-C at the pre-screening visit (<100 mg/dL, ≥100 mg/dL)*	Other secondary objective
Time to all-cause death	FAS	Log rank test	Geographic region, LDL-C at the pre-screening visit (<100 mg/dL, ≥100 mg/dL)	Other secondary endpoint
		Cox proportional hazards regression	Treatment group/ geographic region, LDL-C at the pre-screening visit (<100 mg/dL, ≥100 mg/dL)*	Other secondary objective
		Plot of Kaplan-Meier Estimates		Support of other secondary objective
Reasons for all-cause death	FAS		Event rates and 95% CIs	
LDL-C: percent change from baseline to each post-randomization visit	FAS	MMRM	Treatment group, scheduled visit (categorical), baseline value (continuous), treatment × scheduled visit interaction, baseline value × scheduled visit interaction, geographic region, LDL-C at the pre-screening visit (<100 mg/dL, ≥100 mg/dL)	Other secondary endpoint

Endpoint	Analysis Set	Statistical Method	Covariates/ Strata	Objective
		Plot of LS-Mean percent changes from baseline and 95% CI		
LDL-C: nominal change from baseline to each post-randomization visit	FAS	MMRM	Treatment group, scheduled visit (categorical), baseline value (continuous), treatment × scheduled visit interaction, baseline value × scheduled visit interaction, geographic region, LDL-C at the pre-screening visit (<100 mg/dL, ≥100 mg/dL)	Other secondary objective
LDL-C: percent change from baseline to last post-baseline measurement	FAS	ANCOVA	Treatment group, baseline value, geographic region, LDL-C at the pre-screening visit (<100 mg/dL, ≥100 mg/dL)	Supportive of other secondary objective
Total cholesterol: percent change from baseline to each post-randomization visit	FAS	MMRM	Treatment group, scheduled visit (categorical), baseline value (continuous), treatment × scheduled visit interaction, baseline value × scheduled visit interaction, geographic region, LDL-C at the pre-screening visit (<100 mg/dL, ≥100 mg/dL)	Other secondary endpoint
		Plot of LS-Mean percent changes from baseline and 95% CI		
HDL-C: percent change from baseline to each post-randomization visit	FAS	MMRM	Treatment group, scheduled visit (categorical), baseline value (continuous), treatment × scheduled visit interaction, baseline value × scheduled visit interaction, geographic region, LDL-C at the pre-screening visit (<100 mg/dL, ≥100 mg/dL)	Other secondary endpoint
		Plot of LS-Mean percent changes from baseline and 95% CI		

Endpoint	Analysis Set	Statistical Method	Covariates/ Strata	Objective
Triglycerides: nominal change from baseline to each post-randomization visit for log-transformed value	FAS	MMRM	Treatment group, scheduled visit (categorical), baseline value (continuous), treatment × scheduled visit interaction, baseline value × scheduled visit interaction, geographic region, LDL-C at the pre-screening visit (<100 mg/dL, ≥100 mg/dL)	Other secondary objective
Non-HDL-C: percent change from baseline to each post-randomization visit	FAS	MMRM	Treatment group, scheduled visit (categorical), baseline value (continuous), treatment × scheduled visit interaction, baseline value × scheduled visit interaction, geographic region, LDL-C at the pre-screening visit (<100 mg/dL, ≥100 mg/dL)	Other secondary endpoint
		Plot of LS-Mean percent changes from baseline and 95% CI		
VLDL-C: percent change from baseline to each post-randomization visit	FAS	MMRM	Treatment group, scheduled visit (categorical), baseline value (continuous), treatment × scheduled visit interaction, baseline value × scheduled visit interaction, geographic region, LDL-C at the pre-screening visit (<100 mg/dL, ≥100 mg/dL)	Other secondary endpoint
RLP-C: percent change from baseline to each post-randomization visit	FAS	MMRM	Treatment group, scheduled visit (categorical), baseline value (continuous), treatment × scheduled visit interaction, baseline value × scheduled visit interaction, geographic region, LDL-C at the pre-screening visit (<100 mg/dL, ≥100 mg/dL)	Other secondary endpoint
Apo-A-I: percent change from baseline to each post-randomization visit	FAS	MMRM	Treatment group, scheduled visit (categorical), baseline value (continuous), treatment × scheduled visit interaction, baseline value × scheduled visit interaction, geographic region, LDL-C at the pre-screening visit (<100 mg/dL, ≥100 mg/dL)	Other secondary endpoint

Endpoint	Analysis Set	Statistical Method	Covariates/ Strata	Objective
Apo-B: percent change from baseline to each post-randomization visit	FAS	MMRM	Treatment group, scheduled visit (categorical), baseline value (continuous), treatment × scheduled visit interaction, baseline value × scheduled visit interaction, geographic region, LDL-C at the pre-screening visit (<100 mg/dL, ≥100 mg/dL)	Other secondary endpoint
Lp(a): percent change from baseline to each post-randomization visit	FAS	MMRM	Treatment group, scheduled visit (categorical), baseline value (continuous), treatment × scheduled visit interaction, baseline value × scheduled visit interaction, geographic region, LDL-C at the pre-screening visit (<100 mg/dL, ≥100 mg/dL)	Other secondary endpoint
Lp(a): nominal change from baseline to each post-randomization visit in log-transformed value	FAS	MMRM	Treatment group, scheduled visit (categorical), baseline value (continuous), treatment × scheduled visit interaction, baseline value × scheduled visit interaction, geographic region, LDL-C at the pre-screening visit (<100 mg/dL, ≥100 mg/dL)	Other secondary objective
hs-CRP: nominal change from baseline to each post-randomization visit for log-transformed value	FAS	MMRM	Treatment group, scheduled visit (categorical), baseline value (continuous), treatment × scheduled visit interaction, baseline value × scheduled visit interaction, geographic region, LDL-C at the pre-screening visit (<100 mg/dL, ≥100 mg/dL)	Other secondary objective

* If model fitting of the Cox proportional hazards regression model fails to converge, LDL-C at pre-screening will be removed as a stratification factor.
 
FAS = Full Analysis Set SAS = Safety Analysis MMRM = Mixed Model Repeated Measures CI = confidence interval ANCOVA = analysis of covariance
				

